8.4 Statistical/Analytical Issues

8.4.1 Adjustments for Covariates

No adjustment for covariates is planned.

8.4.2 Handling of Dropouts or Missing Data

[figure not shown]
All data obtained will be used in the analysis and no imputation will be carried out for missing data.

8.4.3 Data Review

In order to perform the statistical analysis of the main objective analysis, a decision needs to be made *on evaluability of patients and visits prior to locking the database and breaking the code for the blinded study medication*. In particular, data situations constituting protocol deviations may need to be defined. This will be done at the Blind Data Review Meeting.

Performance of Blind Data Review Meeting for the main objectives analysis will require a clean database, i.e. all data are available and coded and no data queries are open (on safety and efficacy data up to Week 12 and all AE data documented until the date of data base soft lock).

No data entry should be performed between the data base Soft Lock for Main Objectives analysis and database lock for Main Objective Analysis. Exception would be Queries, which raised during the BDRM requiring a solution before data base Lock.

A reduced Data Review will be performed before the data base lock for the final analysis focusing on review of data issues. More details on scope and performance of data review meetings will be described in a separate BDRM plan.

[figure not shown]
After the BDRM is performed, all decisions will be summarized in BDRM Minutes, which will be approved before the database will be locked for the analysis.

8.4.4 Multicentre Studies

Not applicable since this is a monocentric study.

8.4.5 Multiplicity of Endpoints

Due to this is being a Phase I safety and tolerability study, no adjustment of any p-values will be made to account for inflation of the Type 1 error rate arising from multiple endpoint testing.

9 Main Objective and Final Analyses

9.1 Main Objective Analysis

The database will be locked after all patients have completed their Week 12 Visit and main objectives analysis will be performed on unmasked data.

For visit-based tables, only study visits up to Week 12 will be presented for the analysis. However, for event-type data (i.e. adverse events and concomitant medication) and the assessment of primary safety outcomes (i.e. AE, BCDVA, ERG, OCT and HVF assessments), also data AFTER Week 12 Visit will be considered.

For the listings, all data as recorded in the data base will be reported. Respective footnotes will be added to the output to indicate that calculated figures of data after Week 12 needs to be considered as preliminary. As a consequence, interpretation of provided TLFs in the CSR should focus on the results of data assessed before Week 12.

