Table 2: Study Visits

Scheduled Visit	Scheduled Visit Label	Scheduled Study Day	Visit Window
Screening Visit	Screening	Before Baseline Visit	Up to 4 weeks before date of Baseline Visit
Baseline Visit Day 0	Baseline	0	Date of Baseline Visit – Date of First Study Treatment in [-1, 0]
Week 1	Week 1	7	Visit date – Date of First Study Treatment in [5 – 9]
Week 4	Week 4	28	Visit date – Date of First Study Treatment in [24 – 32]
Week 8	Week 8	56	Visit date – Date of First Study Treatment in [49 – 63]
Follow-up Visit Week 12	Week 12	84	Visit date – Date of First Study Treatment in [77 – 91]
Follow-up Visit Week 32	Week 32	224	Visit date – Date of First Study Treatment in [217 – 231]
Documented unscheduled Visits will be labeled as “Unscheduled Visit x.01”, “Unscheduled Visit x.02”, “Unscheduled Visit y.01”... .			
Date of First Study Treatment is to be taken from eCRF page “Study Drug Dosing Dates”.			

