7.2.7 Primary Safety Outcomes

The primary safety outcomes of the study are:

Unexpected severe progression of optic neuropathy (USPON)

Unexpected Severe Progression of Optic Neuropathy will be measured a) by a central vision loss; b) by visual field testing; and/or c) by examination of the optic nerve. It is recorded per eye on the Follow-Up Visits of the eCRF pages 'Best Corrected Distance Visual Acuity', 'Humphrey Visual Field Monitoring', 'Electroretinography' and Ocular coherence tomography' via a tick box 'Was an unexpected severe progression measured...' (Yes/No).

USPON will be investigated only for treated eyes, i.e. if an eye is not treated, the respective tick box will not be considered for definition of primary outcome.

[figure not shown]
For a patient, USPON occurred, if in any of the following assessments the respective question on unexpected severe progression is answered 'Yes':

- a) from BCDVA assessments: eCRF question is ticked 'Yes' for at least one treated eye at any Follow-Up Visit after first study treatment administration (including unscheduled visits).
- b) from HVF assessments: eCRF questions is ticked 'YES' for at least one treated eye in at least one assessment during Treatment or Follow-Up Period (i.e. performed after first study treatment administration). An assessment is considered as performed during Follow-Up Period, if Test Date and Test time as documented on eCRF Page 'Humphrey Visual Field Monitoring' was after Week 8 Visit (See also Section 7.2.9 for Details).
- c) from ERG assessments: eCRF question is ticked 'Yes' for at least one treated eye at any Follow-Up Visit after first study treatment administration (including unscheduled visits).
- d) from OCT assessments: eCRF question is ticked 'Yes' for at least one treated eye at any Follow-Up Visit after first study treatment administration (including unscheduled visits).

As supportive variable, the occurrence of USPON during Treatment Period will be derived, which is defined as an USPON, which was recorded between the first study treatment administration and Week 8 Visit/Study termination Visit (for patient withdrawn during the treatment period).

Intolerance or allergy to the drug

The occurrence of intolerance and allergy to the drug will be identified during the BDRM by reviewing reported Preferred Terms of Treatment Emergent Adverse Events (for definition see Section: 7.2.10).

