- An AE leading to study discontinuation is defined as an AE where in the eCRF section 'Action regarding Patient' the box 'Patient Withdrawn' is ticked (this should match with the primary reason for early withdrawal of 'Adverse Event' on the End of Study eCRF page).
- An AE is classified as 'Related' to Study Treatment if the relationship to study medication recorded as 'Possible' or 'Probable' or 'Highly Probable'. An AE will be classified as unrelated to study medication if the relationship to study medication was recorded as 'None' or 'Unlikely'. AEs with missing relationship to study treatment will be counted as 'Related' to Study Treatment.
- A Fatal AE is defined as an AE where the outcome is recorded as 'Fatal'.

These definitions will apply accordingly also for the subsequent sub-classes of AEs.

Non Treatment-emergent adverse events (Non-TEAEs)

A Non-TEAE is defined as any AE, which started before the first administration of study treatment. An AE is considered as Non-TEAE, if the eCRF question 'Did the event occur:' was answered with 'Before Treatment Period'.

Treatment-emergent adverse events (TEAEs)

A treatment-emergent adverse event is defined as an AE that started on or after the date of the First Study Treatment Administration. An AE is considered as TEAE, if the eCRF question 'Did the event occurred:' was answered either with 'During Treatment Period' or 'During Follow-Up Period'.

TEAEs in Treatment Period

This is defined as a TEAE (as defined above) that started on or after the date of the First Study Treatment Administration but on or before the Week 8 Study Visit. A TEAE in

Treatment Period will be identified, if the eCRF question ‘Did the event occurred:’ was answered with ‘During Treatment Period’.

TEAEs in Follow-Up Period

This is defined as an TEAE with a start date after the Week 8 Visit. An TEAE will be considered as TEAE in Follow-Up Period, if eCRF question ‘Did the event occur:’ was answered with ‘During Follow-Up Period’.

For listing purposes, treatment day of onset of AE will be derived according to the definition given in section 7.1.

Missing Codes or Incomplete AE start dates:

In the event that coding information will not be available for a specific AE, the event will be presented as ‘Uncoded Event’. However, for final TLFs it is anticipated that all events are coded.

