8.1 General Methods

For the study, both eyes are under investigation. For analysis purposes all eye-related assessments will be displayed separately by Primary/Secondary Eye. Untreated eyes will not be considered for analysis and be listed only indicated with 'Untreated'.

For continuous variables, the mean, standard deviation, minimum, median and maximum will be presented by treatment group, together with the total number of observations and the number of missing and non-missing values. Unless otherwise specified minimum and maximum values will be reported to the same number of decimal places as the recorded measurements, mean and median are reported to one more decimal place and standard deviation one additional decimal place more than the mean.

For categorical variables, absolute and relative frequencies will be reported by treatment group. Relative frequencies will be based on all observations and reported as a percentages to one decimal place. Unless otherwise specified, percentages will be based on the number of patients with data in the considered analysis set and will not be calculated for missing categories.

Incidences over a specific time interval like adverse events, medical history and concomitant medication will be reported on a patient basis. The percentages will be calculated using the number of patients in the treatment group for the considered analysis set as denominator. For the presentation of incidences during the Follow-Up Period, the SAF-F set will be used, which results in a reduction of the denominator to the number of patients in the SAF, who have entered the Follow-Up Period.

All hypotheses will be tested at a 5% level of significance using a two-sided test.

P-values will be rounded to three decimal places. If a p-value is less than 0.001 it will be reported as "<0.001." If a p-value is greater than 0.999 it will be reported as ">0.999.

Statistical significance will be declared if the rounded p-value will be less than 0.050 unless stated otherwise. Two-sided 95% confidence intervals of the differences between the treatment groups will be calculated as indicated in sections 8.2 and 8.3.

Post-Text TLFs will be provided in collated electronic MS Word .rtf files (i.e. table columns and rows appear as free text instead of MS Word Table format).

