10.6 Primary Study Outcomes

10.6.1 Primary Safety Outcomes

The incidence of USPON, USPON during treatment period, Intolerance/Allergy to the drug, Unexpected Related AEs affecting ocular function/eye pressure, Local toxicities and systemic toxicities will be summarized for SAF by counts and percentages of affected patients per treatment group. In addition, number of reported events will be provided.

A listing will be provided for the SAF summarizing all incidences on the patient level. The original source of presented events will be flagged in respective listings for AEs, BCDVA, HVF, ERG and OCT, respectively.

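### The main analysis counts USPON and intolerance/allergy past Week 12 over unequal follow-up, and no table gives the Week 12 result that SAP 9.1 tells readers to focus on

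*SAP*

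**What the plan says.** **Data cut.** SAP 9.1 locks the database once every patient has completed Week 12. It limits visit-based tables to Week 12 but treats event-type data and the primary safety outcomes differently: "also data AFTER Week 12 Visit will be considered". Figures that use later data are to be footnoted as preliminary, and "interpretation of provided TLFs in the CSR should focus on the results of data assessed before Week 12".

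**Outcome definitions.** Under SAP 7.2.7, USPON on the visual acuity, ERG or OCT page counts if it is ticked "for at least one treated eye at any Follow-Up Visit after first study treatment administration (including unscheduled visits"; visual field assessments count throughout treatment and follow-up. A supportive variable restricts USPON to the treatment period. Intolerance/allergy "will be identified during the BDRM by reviewing reported Preferred Terms of Treatment Emergent Adverse Events". SAP 7.2.10 sets only a start for those events: "A treatment-emergent adverse event is defined as an AE that started on or after the date of the First Study Treatment Administration".

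**Presentation.** SAP 10.6.1 lists the rows of the primary safety table, beginning "The incidence of USPON, USPON during treatment period, Intolerance/Allergy to the drug", as counts and percentages of affected patients. On the denominator, SAP 8.1 says: "The percentages will be calculated using the number of patients in the treatment group for the considered analysis set as denominator". SAP 8.2 plans no inference for these outcomes.

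**Final analysis.** Under SAP 9.2 the results after all Week 32 visits go into an addendum to the CSR. In section 12, Table 14.2-1.1 is repeated for that analysis (SR = Y), but the patient-level Listing 16.2.6-1.1 is not (SR = N).

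**The concern.** A percentage of patients affected is a risk only if it refers to a stated time. At the main lock the last patient has 12 weeks of follow-up and early patients may have up to 32, yet all enter one count over one denominator. The result mixes time horizons in proportions set by the speed of enrolment.

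SAP 9.1 recognises that the later data are immature and points the reader to Week 12, but the table merges the two parts, and a footnote cannot separate them. Safety and tolerability are the primary objective. Because these outcomes are described and not tested, the absolute rates are the reported result, and they are what a later trial or another rhNGF study would compare against.

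The other two primary safety outcomes are not at issue: SAP 7.2.7 expects the investigator to flag them only during treatment.

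**Working it through.** **1. Is there a Week 12 result anywhere in the planned output?**

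| Output | Window | Gives Week 12? |
|---|---|---|
| Table 14.2-1.1, USPON | first dose to lock | No |
| Table 14.2-1.1, USPON in treatment period | to Week 8 or termination visit | No |
| Table 14.2-1.1, intolerance/allergy | first dose to lock, no split | No |
| Tables 14.3.1-10.1 to -12.1, treatment-period TEAEs | to Week 8 | No |
| Tables 14.3.1-13.1 to -15.1, follow-up TEAEs | after Week 8, no end | No |
| Table 14.1-7.1, exposure | follow-up duration per arm | Not an incidence |

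**2. How unequal is follow-up?** The plan has no figure to reproduce here. Inputs from the documents: 60 patients (40:20), main lock at the last Week 12 visit, last visit at Week 32. Assumed: 60 entries evenly spaced over an accrual of A weeks, and no dropout.

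Follow-up at lock = min(32, 12 + A − entry week). A patient has reached Week 32 if the entry week is at or before A − 20. With entries at A × i/59 (i = 0 to 59), this means i ≤ 59 × (1 − 20/A):
- A = 13: nobody; the longest follow-up is 12 + 13 = 25 weeks
- A = 26: i ≤ 13.6, so 14 patients
- A = 52: i ≤ 36.3, so 37 patients
- A = 104: i ≤ 47.7, so 48 patients

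**3. What would the table show for USPON?** Assume that a proportion p has the event by Week 12. The weekly hazard is h = −ln(1 − p)/12, multiplied by k after Week 12, so cumulative incidence at t > 12 is CI(t) = 1 − exp(−12h − k·h·(t − 12)).
- *Lower bound* (later events found only at the Week 32 visit): p + (n32/60) × (CI(32) − p), where n32 is the number at Week 32.
- *Upper bound* (later events recorded as they occur, for example at unscheduled visits): mean of CI(follow-up at lock) over the 60 patients.

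For p = 5% and k = 1: h = −ln(0.95)/12 = 0.004274 and CI(32) = 1 − exp(−0.004274 × 32) = 12.78%. At A = 26 the lower bound is 5 + (14/60) × 7.78 = 6.82%. For k = 0.5, CI(32) = 8.98%.

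| Accrual (weeks) | k = 1, lower to upper | k = 0.5, lower to upper |
|---|---|---|
| 13 | 5.00% to 7.59% | 5.00% to 6.31% |
| 26 | 6.82% to 9.82% | 5.93% to 7.45% |
| 52 | 9.80% to 11.27% | 7.45% to 8.20% |
| 104 | 11.23% to 11.99% | 8.18% to 8.57% |

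A fixed Week 12 cut gives 5.00% in every row. In patients, at k = 1 (arm size × shift):
- A = 26: 0.73 to 1.93 extra of 40 on active, 0.36 to 0.96 of 20 on vehicle
- A = 52: 1.92 to 2.51 extra of 40, 0.96 to 1.25 of 20

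**4. Intolerance/allergy.** Drug stops at Week 8, so the later hazard should be low. With p = 10% and events recorded as they occur, accrual of 13, 26, 52 and 104 weeks gives 10.51%, 10.96%, 11.26% and 11.41% for k = 0.1, and 11.27%, 12.38%, 13.11% and 13.47% for k = 0.25.

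**5. Between arms.** Randomization makes the expected difference in mean follow-up zero. Permuting the 40:20 split gives a chance difference (95th percentile of the absolute value) of 3.6 weeks at A = 26 and 3.3 weeks at A = 52.

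**The case against.** The choice is deliberate and disclosed. Reporting every sight-threatening event known at a lock is a defensible safety convention, and SAP 9.1 adds footnotes and guidance on interpretation. That is a reason to keep the later events visible, not to leave out the result the guidance points to.

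Other points on that side:
- **On-treatment rates exist.** USPON to Week 8 is tabulated, and intolerance/allergy to Week 8 could be approximated from Table 14.3.1-10.1. Both are free of accrual effects, but neither is the Week 12 result.
- **The listings allow a hand count.** With 60 patients and few events this is feasible. But SAP 5.3 requires double programming for the primary endpoint tables and none for listings, so a hand count is not a planned or checked result.
- **The table shells are in a separate document not provided.** They could contain a Week 12 row, but section 10.6.1 sets the table content and names none.
- **The final analysis has a common horizon.** It does, at Week 32, later and in an addendum. That answers a different question.
- **The size is assumed.** This stands. After Week 12, visual acuity, ERG and OCT are next scheduled at Week 32, and procedures at unscheduled visits are at the investigator's discretion. For USPON the truth probably lies nearer the lower bound, which is zero shift at 13 weeks of accrual.
- **No test is affected.** This also stands: type I error is not in question, and no systematic bias between arms follows.

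**Conclusion.** The concern holds. For two primary safety outcomes, the main-analysis table reports a proportion with no defined time horizon, and the Week 12 result that SAP 9.1 makes the focus is not produced. This follows from the SAP text and needs no assumption.

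The size cannot be fixed from the documents; it depends on accrual time, event rate, later hazard and how later events are detected. Under the assumptions shown, a 5% USPON rate at Week 12 would appear as anything from 5.0% to 12.0%. Intolerance/allergy would move less, by 0.5 to 3.5 percentage points from 10%. The damage is to absolute rates in the CSR. It is worth correcting before the main lock, because the remedy is cheap and the outcomes are primary. The SR mismatch between Table 14.2-1.1 and Listing 16.2.6-1.1 is a separate clerical point.

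**What to change.** - In Table 14.2-1.1, add rows for USPON and for intolerance/allergy from first dose through each patient's Week 12 visit, and name them the main-analysis result. For a patient without that visit, cut at 91 days after first dose, the end of the Week 12 window in SAP Table 2 (Treatment Day 92 under the SAP's plus-one numbering).
- Show events after Week 12 in an adjacent row marked preliminary, so that none is dropped.
- Keep the full Week 32 figure in the final analysis.
- Set Listing 16.2.6-1.1 to SR = Y.
- State that the intolerance/allergy preferred-term rule fixed at the masked data review applies unchanged to later TEAEs, unless the separate review plan, which was not provided, already says so.

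The cost is SAP wording, a few rows in one table and one listing rerun. The table becomes slightly longer with small counts, and its headline rows leave out later events, which the adjacent row shows.

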9.2 Final Analysis

At the end of the study (i.e. after all patients have completed Week 32 Visit), an updated analysis will be performed presenting the complete study data. Section 12 indicates which TLFs will be reproduced because they will contain additional data from the period after the first 12 weeks until Week 32. These newly produced TLFs will be reported in a Statistical Report that is to be considered as an addendum to the CSR.

10 Overview of Tables, Listings and Figures

In this section, TLFs will be presented content wise. The full set of TLFs will be tabulated in section 12, where it will also be indicated whether the item is unique (or first mentioned) or a repeat. Mock shells for unique TLFs will be presented in a separate document.

10.1 Disposition of Patients

[figure not shown]
Patient disposition data will be collected on the 'End of Study' eCRF page when a patient completed or discontinued from the study. Whether the patient completed the study is recorded along with the single primary reason for withdrawal. It is also recorded whether the emergency envelope was opened during the study and if so, the date and reason of unmasking has been provided.

A disposition summary of patients includes the number (n) and percentage (%) of patients in all analysis sets defined in Section 6.1. All percentages will be based on the number of patients randomized, i.e. ITT. Percentages will not be shown for the Total Set.

The primary reason for study discontinuation will also be summarized for the ITT separately by study periods providing counts (n) and percentages (%). This summary will also include counts and percentages for unmasking.

A listing presents for the ITT the randomized allocation to study treatment as well as dispensing of kit numbers. Furthermore, a listing is provided displaying assignment of patients to SAF and ITT.

For the Total Set, a listing will be provided by summarizing study termination/completion information, date of informed consent (from eCRF page 'Informed Consent'), unmasking information and duration of study periods.

10.2 Protocol Deviations

The number of patients who had at least one CSR reportable protocol deviation and all categories of Protocol Deviations will be summarized by counts (n) and percentages (%) for the ITT. Percentages will be calculated based on the number of patients in the ITT.

A listing presents all Protocol Deviation data for the ITT.

10.3 Inclusion and Exclusion Criteria

The eligibility of all patients for entry into the study will be assessed at the Screening visit and confirmed at the Day 0 Therapy Initiation visit by the inclusion and exclusion criteria ('Inclusion/Exclusion Criteria' eCRF page).

Two listings will be provided for all patients in the ITT displaying status of Inclusion and Exclusion criteria, respectively.

10.4 Demographic and Other Baseline Characteristics

10.4.1 Demographic Characteristics

The following demographic variables will be collected on eCRF page 'Demography' or derived as detailed in section 7.2.2: Date of Birth, Gender ('Male', 'Female'), Race ['White', 'Black or African American', 'Asian', 'Native Hawaiian or Other Pacific Islander', 'American Indian or Alaska Native' or 'Other (with specification text box)'], Ethnicity ('Hispanic, Latino or Spanish', 'Not Hispanic, Latino or Spanish'), Age at Screening (years).

Demographic data including collected and derived, continuous and categorical variables will be summarized per treatment group and overall by summary statistics or absolute counts (n) and percentages (%) for the SAF.

A listing presents all demographic data for the ITT.

